## Schedule of assessments/events for all visits

### *Initial study visit*

This visit will comprise subject consent and screening.

Subjects will receive their initial screening and be consented by an IHTC staff member/clinician. Screening is expected to take up to 10 days but may be shorter depending on return of required laboratory testing.

The screening visit will include obtaining informed consent; performance of a physical examination, vital signs (blood pressure, pulse, temperature, and respiratory rate) and weight measurement; initiation of safety data collection; and the review/collection of clinical and laboratory data (adequate data in the subject's recent medical files may negate the running of some of laboratory tests) including:

- Baseline FVIII, \* aPTT, PT and VWF:Ag
- Baseline FVIII inhibitor level
- Baseline CBC w/diff and CMP + direct bilirubin

---

\* If the subject has an inhibitor, then testing for FVIII level may not be medically necessary as FVIII is usually undetectable in such cases. Exceptions exist, such as for a patient who has mild hemophilia with an inhibitor that only recognizes infused FVIII and not endogenous FVIII.

- Serum pregnancy test for female subjects
- Documentation of current or past infection of Hepatitis A, B and C (tests listed below). If documentation is not available, then the tests will be administered as part of the screening process\*
  - HAV:Ab
  - HBV:Ag and Ab (Core and Surface); if HBV:Ag positive, HBV viral load
  - HCV:Ab; if HCV:Ab positive, HCV viral load
- Documentation of HIV infection (if Ab positive, viral load and CD4 count)
- Obtain baseline Haem-A-QoL and EQ-5D-5L
- If an activity monitoring device is standardly utilized by the patient, then permission will be requested to access data for the 1-month period prior to study entry and use of data from the device if continued during the study
- Review of at least 16 weeks, and up to 6 months if available, of data on prior use of hemostatic therapy and number of breakthrough bleeding events
- Review of 6 months of data on prior need for hospitalization or for PRBC transfusion
- Review of therapy prior to study entry with dose and interval and trough level if available on prophylaxis
- Review of history of inhibitor including date of first positive test, highest documented titer and date
- Review of concomitant medications and supplements
- Date of development or identification of pseudotumor and documentation of radiologic (CT or MRI) scans
- Review of surgeries and procedures

*Second study visit (up to 10 days from screening visit)*

The study visit will comprise a 4-week period to administer the 4 loading doses of Hemlibra (emicizumab). This study visit will take place at the IHTC.

- Vital signs (blood pressure, pulse, temperature, and respiratory rate) and weight
- Baseline anti-drug antibody levels for Hemlibra (emicizumab) – banked plasma sample

---

\* Although this testing and documentation is considered standard of care, there are important reasons to include this in the study and budget. There are patients in the US who are not followed at a federally recognized hemophilia treatment center and this testing may be inconsistently available. In addition, there are patients who refuse entry into CDC studies where this testing is performed or refused vaccination to prevent Hepatitis A and/or B transmission. Knowing each patient's viral exposure status and vaccination history will be important to decrease risk of community acquired infections that may lead to development of AEs that could be avoided.

- Dispensation of a suitable quantity of Hemlibra (emicizumab) (quantity to be determined by the Study Investigator)
- Baseline radiology (CT or MRI) if not performed within one month of study entry or provided scans are deemed inadequate to accurately assess the extent of the pseudotumor
- Weeks 1-4
  - First 4 weekly loading doses to be administered at IHTC
- Week 4
  - Anti-drug antibody levels for Hemlibra (emicizumab) – banked plasma sample
  - Obtain data if applicable from an activity monitoring device if standardly utilized by the patient

*Subsequent study visits (annual and study close-out visits at the IHTC; other study visits with local physician)*

Subsequent study visits will occur once a quarter, as is the standard of care for patients with hemophilic pseudotumor. These study visits will take place at the medical facilities of the subject's local physician, except for the annual and study close-out visits, which will take place at the IHTC. The first subsequent study visit will be 3 months ( $\pm 2$  weeks) following the first loading dose of Hemlibra (emicizumab).

The specific requirements of each visit are listed below. Depending on when a subject enrolls and when the study ends, the subject might not participate in all study visits beyond month 24.

*Study visits at months 3, 9, 15, 21, 27, 33, 39 and 45 ( $\pm 2$  weeks)*

The subject will follow-up with their local physician at the intervals specified above.

During this visit:

- Vital signs (blood pressure, pulse, temperature, and respiratory rate) and weight
- Review of patient diary for completeness
- Patient study documentation will be submitted to the IHTC for review of compliance and data collection
- Review of AEs
- Review of concomitant medications and supplements
- Data will be obtained from an activity monitoring device if standardly utilized by the patient (if applicable)

*Study visits at months 6, 18, 30 and 42 ( $\pm 2$  weeks)*

The subject will follow-up with their local physician for a more detailed clinical review at the intervals specified above.

During this visit the following data will be collected and/or reviewed and transmitted to the IHTC:

- CBC panel w/diff
- Vital signs (blood pressure, pulse, temperature, and respiratory rate) and weight
- Review of breakthrough bleeding events requiring alternate hemostatic therapy
- Review of the number of hospital admissions
- Review of the development of anemia requiring transfusion or intervention
- Review of AEs
- Review of concomitant medications and supplements
- Review of patient diary for completeness
- Patient study documentation will be submitted to the IHTC for review of compliance and data collection
- Data will be obtained from an activity monitoring device if standardly utilized by the patient (if applicable)

*Annual study visits (months 12, 24 and 36 ±2 weeks)\**

The annual study visit will take place at the IHTC.

During this visit the following data will be collected and/or reviewed at the IHTC:

- Radiologic evaluation (CT and/or MRI) to evaluate control of progression, stabilization or regression (ie changes in size) of the pseudotumor
- Vital signs (blood pressure, pulse, temperature, and respiratory rate) and weight
- Anti-drug antibodies (banked plasma sample)
- Repeated Haem-A-QoL and EQ-5D-5L
- CBC panel w/diff
- Review of breakthrough bleeding events requiring alternate hemostatic therapy
- Review of the number of hospital admissions
- Review of the development of anemia requiring transfusion or intervention
- Review of concomitant medications and supplements
- Review of AEs
- Review of patient diary

---

\* Subjects enrolled in the study for the maximum length of time (ie, 48 months) will also participate in an annual visit at approximately the 48-month time point; however, this will be the subject's close-out visit, and the procedures required will be those listed in **Section 7.5**. The primary difference between an annual visit and the close-out visit is the collection of used and unused vials of Hemlibra (emicizumab), rather than the dispensation of additional drug

- Patient study documentation will be collected for review of compliance and data collection
- Data will be obtained from an activity monitoring device if standardly utilized by the patient (if applicable)

During this annual visit, a physical examination will be performed, used/empty vials of Hemlibra (emicizumab) will be collected and a suitable quantity of Hemlibra (emicizumab) will be dispensed.

#### *Unscheduled study visits*

- Any unscheduled study visits with the subject's local hemophilia physician will be recorded in the CRF along with all relevant medical information (eg, reason for visit, diagnoses, scans, AEs, lab results, vital signs [blood pressure, pulse, temperature, and respiratory rate], weight, etc)
- If a subject meets with a physician other than their local hemophilia physician, that information should be communicated to their hemophilia physician at the next scheduled quarterly study visit and appropriate medical information recorded in the CRF
- Hospitalizations should be recorded in the CRF along with relevant medical information (see **Section 6.11.3.2d**). These should be reported to the IHTC within 7 days of their occurrence

#### *Surgeries*

- All surgeries will be recorded in the CRF, which should minimally include the following information (see **Section 6.11.3** for additional reporting requirements):
  - Procedure type
  - Reason for procedure
  - Planned or unplanned
  - Date of procedure and length of hospitalization
  - Hemostatic therapy provided pre-procedure (type, dose and dates)
  - Hemostatic therapy provided post-procedure (type, dose and dates)
  - Hemostatic outcome immediately post-procedure
  - Hemostatic outcome at the end of hospitalization
  - Adverse events experienced (including, but not limited to clots, thromboses and TMA)
  - Vital signs (blood pressure, pulse, temperature, and respiratory rate) and weight

### *Study close-out visit*

A study close-out visit will occur at the IHTC for all subjects during the final 2 months prior to the anticipated study termination date.

During this close-out visit the following data will be collected and/or reviewed at the IHTC (depending on when the most recent annual visit took place and at the Study Investigator's discretion, not all specified items may be necessary):

- Radiologic evaluation (CT and/or MRI) to evaluate control of progression, stabilization or regression of pseudotumor
- Vital signs (blood pressure, pulse, temperature, and respiratory rate) and weight
- Anti-drug antibodies (banked plasma sample)
- Repeated Haem-A-QoL and EQ-5D-5L
- CBC panel w/diff
- Review of breakthrough bleeding events requiring alternate hemostatic therapy
- Review of the number of hospital admissions
- Review of the development of anemia requiring transfusion or intervention
- Review of AEs
- Review of concomitant medications and supplements
- Review of patient diary
- Patient study documentation will be collected for review of compliance and data collection
- Data will be obtained from an activity monitoring device if standardly utilized by the patient (if applicable)

Additionally, a physical examination will be performed and all used and unused vials of Hemlibra (emicizumab) will be returned to the IHTC.

Following the close-out visit, all subjects will be requested to meet with their local hemophilia physician to determine their ongoing treatment therapy/regimen.

## **Dosing Regimen**

### *Genentech drug product*

Once weekly US-labeled Hemlibra (emicizumab) using FDA-approved dosing regimen

- Four loading doses: 3 mg/kg once weekly by subcutaneous injection
- Subsequent doses: 1.5 mg/kg once weekly by subcutaneous injection
- *Dose escalation: Should a subject have suboptimal control of breakthrough bleeding (ie, 2 qualifying bleeds within 24 weeks) while on 1.5 mg/kg once weekly Hemlibra*

*(emicizumab) prophylaxis, the dose may be increased to 3 mg/kg once weekly Hemlibra (emicizumab) prophylaxis upon approval of the Study Investigator (Section 5.3.3). If this 3 mg/kg maintenance dose does not result in an improvement in breakthrough bleeding, the subject may return to the standard 1.5 mg/kg maintenance dose upon approval of the Study Investigator, assuming this 1.5 mg/kg dose had resulted in an improvement in breakthrough bleeding compared to their pre-study regimen.*

#### *Non-Genentech drug products*

##### Non-inhibitor subjects and low titer inhibitor subjects (titer <5 BU)

- Breakthrough bleeding events should be treated with a FVIII concentrate, rFVIII or pdFVIII, using the local standard of care at the lowest level expected to achieve hemostasis
- If the subject's standard of care for treatment of bleeding events with low titer inhibitors is a bypassing product, the subject will follow treatment as outlined under high titer inhibitors

##### High titer inhibitor subjects (titer ≥5 BU)

- Breakthrough bleeding events should be treated with rFVIIa as first line therapy using the local standard of care. aPCC (<100 U/kg/day for preferably no more than 1 day) may only be used upon approval of the Study Investigator and under the supervision of a physician

#### **Dispensation of Hemlibra (Emicizumab)**

A suitable quantity of Hemlibra (emicizumab) (to be determined by the Study Investigator) will be dispensed to each subject at study visit 2 and at all annual visits. If necessary, additional Hemlibra (emicizumab) will be dispensed and shipped throughout the year to ensure the subject has a continuous supply.

#### **Duration of Treatment per Subject**

Minimum 2 years; maximum 4 years. No follow-up period is planned.

#### **Statistical Considerations**

##### *Sample size*

Sample size of approximately 10 subjects is based on clinical feasibility and availability of subjects with hemophilia A and pseudotumor rather than statistical considerations.

##### *Statistical Analyses*

Continuous variables will be summarized by descriptive statistics. Categorical variables will be presented with the number and percentage in each category.

### *Efficacy Analyses*

The primary outcome for this study is bleeding events specifically related to the pseudotumor over time; total bleeding events will also be recorded and analyzed. Hemostatic efficacy is defined as the rate of breakthrough bleeding related to the pseudotumor (the number of bleeding episodes while on Hemlibra that require alternative hematinic therapy). Sample size is determined based on clinical feasibility rather than statistical considerations, accounting for the likely possibility of very few bleeding events, the limited number of available subjects with hemophilia A and pseudotumor, and the need to collect sufficient data to assess safety and efficacy.

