## 6.11 Safety Reporting of Adverse Events

### 6.11.1 Assessment of Safety

Events that are clearly consistent with the expected pattern of progression of the underlying disease should not be recorded as adverse events. These data will be captured as efficacy assessment data only. In most cases, the expected pattern of progression will be based on radiologic (CT and/or MRI) scans. In rare cases, the determination of clinical progression will be based on symptomatic deterioration. However, every effort should be made to document progression through use of objective criteria. If there is any uncertainty as to whether an event is due to disease progression, it should be reported as an adverse event.

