#### 6.11.1.2 *Adverse events*

An AE is any unfavorable and unintended sign (including an abnormal laboratory finding), symptom, or disease temporally associated with the use of an investigational medicinal product (IMP) or other protocol-imposed intervention, regardless of attribution.

This includes the following:

- AEs not previously observed in the subject that emerge during the protocol-specified AE reporting period, including signs or symptoms associated with hemophilia that were not present prior to the AE reporting period
- Complications that occur as a result of protocol-mandated interventions (eg, invasive procedures such as cardiac catheterizations)
- If applicable, AEs that occur prior to assignment of study treatment associated with medication washout, no treatment run-in, or other protocol-mandated intervention
- Preexisting medical conditions (other than the condition being studied) judged by the Study Investigator to have worsened in severity or frequency or changed in character during the protocol-specified AE reporting period

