## 7.2 Study Visit 2: Loading Doses

Study visit 2 will comprise 4 weeks during which the 4 loading doses of Hemlibra (emicizumab) will be administered. During study visit 2, baseline radiology (CT and/or MRI scan) will be acquired if they were not performed within 1 month of study entry and if they are not considered suitable for study purposes. The subject and/or caregiver will also be trained for self-infusion of Hemlibra (emicizumab) and trained to look for signs of adverse events.

Subjects/caregivers will be instructed on how to recognize signs/symptoms of hypersensitivity (including anaphylaxis) and obtain emergency care in the event of such reactions occurring. The Study Investigator has the discretion to provide additional training or include additional observation (eg, after the fourth loading dose), if deemed appropriate, and each subject/caregiver will be able to ask any question he or she may have prior to being deemed capable of performing subcutaneous Hemlibra (emicizumab) injections. If, despite additional training, the investigator

---

\* Vaccinations will not be charged to the study

determines that the subject/caregiver is unable to inject Hemlibra (emicizumab), a trained and proficient caregiver or local healthcare provider should be identified to administer the injections.

Subjects will be observed for a minimum of 30 minutes after the first three loading doses of Hemlibra (emicizumab).

Following each of the first 3 loading doses of Hemlibra (emicizumab), the site will call a subject who has a previous history of a clinically significant hypersensitivity reaction 24 hours after each dose to assess the status of the subject.

Additional precautions following each of these doses may also be considered, including having an extended observation period or IV access prior to dosing, etc. The Study Investigator may include these or other precautions, as deemed appropriate.

A subject utilizing a prophylactic FVIII regimen, a prophylactic bypassing agent regimen or ITI therapy must discontinue those regimens according to the schedule below and for the duration of the study.

- Subjects receiving FVIII prophylaxis must discontinue their FVIII prophylactic regimen immediately prior to their second loading dose of Hemlibra (emicizumab)
- Subjects receiving bypassing agent prophylaxis must discontinue their prophylactic regimen at least 24 hours prior to their first loading dose of Hemlibra (emicizumab)

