### 9.5 Primary Endpoints

The primary endpoints are:

- The number of breakthrough bleeding events over time requiring the use of alternate hemostatic therapy (bleed rate) related to the pseudotumor
- The number of hospital admissions related to the pseudotumor
- The number of incidences of anemia requiring transfusion or intervention related to the pseudotumor
- The control of progression, stabilization or regression of the pseudotumor (ie, changes in size) as measured by yearly assessments including CT and/or MRI

The study investigator will determine whether the reported event was related to the pseudotumor based on a retrospective review of the medical data (eg, bleed location, patient symptoms, etc).

Efficacy analyses will be performed based on the parameters listed above. As there is no control group or placebo in the study, the on-study data will be compared to that listed in the subject's

medical files prior to study enrollment. The efficacy analyses will exclude data acquired during the 4 loading doses (study visit 2). Analyses will be performed on a per-subject basis and in aggregate. Sub-analyses will be considered based upon the included study population.

Demographic and baseline characteristics for all subjects will be summarized using descriptive statistics for continuous variables and frequencies and percentages for categorical variables.

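### The bleed rate is defined over all time on Hemlibra, but 9.5 and 9.6 drop the four loading weeks, so bleeding during the switch shows in no efficacy analysis and some events may count nowhere

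*Combined protocol and SAP*

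**What the plan says.** The synopsis (Efficacy Analyses) states: "Hemostatic efficacy is defined as the rate of breakthrough bleeding related to the pseudotumor", and specifies it as "the number of bleeding episodes while on Hemlibra that require alternative hematinic therapy". The footnotes to the objectives in the synopsis and in Section 2 use the same window. None mentions a loading exclusion. Section 6.10 compares incidence on study with incidence before enrollment, also without an exclusion.

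Section 9.5 narrows the window: "The efficacy analyses will exclude data acquired during the 4 loading doses (study visit 2". Section 9.6 repeats this for the secondary endpoints. Section 7.2 gives the length: "Study visit 2 will comprise 4 weeks during which the 4 loading doses of Hemlibra (emicizumab) will be administered".

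Prior protection is withdrawn around and within those weeks. Under Section 7.2, bypassing prophylaxis stops at least 24 hours before dose 1, ITI stops just before dose 1, and "Subjects receiving FVIII prophylaxis must discontinue their FVIII prophylactic regimen immediately prior to their second loading dose of Hemlibra (emicizumab". Section 5.3.3 places steady state after week 5.

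On safety, Sections 6.11.1 and 6.11.3.2k keep events that plainly follow the expected course of the disease out of the adverse event record: "These data will be captured as efficacy assessment data only". Section 6.11.1.2 lists among adverse events "Preexisting medical conditions (other than the condition being studied) judged by the Study Investigator to have worsened in severity or frequency", a bullet that leaves out the studied disease.

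**The concern.** The primary objective and its analysis use different counting windows. The weeks removed are on-drug weeks in which earlier protection has been or is being withdrawn and the new treatment has not reached steady state. A reader who wants to know what happens to bleeding during the switch will not find it in the analyses of 9.5 or 9.6.

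The safety analysis is the natural fallback, but it is not built for this. The protocol never states whether a breakthrough bleed is an adverse event. Section 9.7 tabulates adverse events by system organ class, preferred term, severity and relationship. It has no split by period and no person-time, so even a bleed recorded as an adverse event gives no loading-phase rate.

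There is also one route by which an event reaches neither analysis. If a loading-phase event is judged to be plain progression, 6.11.1 sends it to efficacy data alone, and 9.5 and 9.6 then exclude it because of its date.

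**Working it through.** The plan states no figure that can be reproduced here. The sample size of about 10 rests on feasibility, and there is no hypothesis test. The check is a comparison of text followed by person-time arithmetic.

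**Text**

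1. Window in the definition: all time on Hemlibra. Window in 9.5 and 9.6: all time on Hemlibra minus study visit 2. These differ.
2. Neither 9.5 nor 9.6 says whether person-time is removed along with the events.
3. Route to neither analysis: 6.11.1 and 6.11.3.2k (not an adverse event, efficacy data only), then 9.5 and 9.6 (dropped from efficacy). Section 9.1 promises summary tables and listings of all data but names no table for this period.

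**Inputs**

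- Loading period L = 4 weeks (Section 7.2; doses on Days 0, 7, 14 and 21).
- Treatment time T = 104 to 208 weeks (2 to 4 years; synopsis, Study Design).
- N = 10 (Section 9.2).
- k = bleed rate in loading divided by the later rate. This is an assumption, because the documents give no rate of pseudotumor-related bleeds before or on treatment.

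**Excluded time**

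- Per subject: L/T = 4/208 = 1.92% to 4/104 = 3.85%.
- All subjects: 10 × 4 = 40 subject-weeks, or 40/52 = 0.77 subject-years, out of 20 to 40 subject-years.

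**Effect on the rate**

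With later rate λ, the from-first-dose rate is [kλL + λ(T − L)]/T. Divided by the post-loading rate λ, this is (kL + T − L)/T. For example, k = 5 and T = 104 give (20 + 100)/104 = 1.154.

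| k | T = 208 weeks | T = 104 weeks |
|---|---|---|
| 0.5 | 0.990 | 0.981 |
| 1 | 1.000 | 1.000 |
| 2 | 1.019 | 1.038 |
| 3 | 1.038 | 1.077 |
| 5 | 1.077 | 1.154 |
| 10 | 1.173 | 1.346 |

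The row k = 10 is what results if subjects bleed at their pre-study rate during loading and the later reduction is 90%.

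If the excluded period were read as ending at the fourth dose (3 weeks), the share would be 1.44% to 2.88%, and the k = 10 range would be 1.130 to 1.260.

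**If events are dropped but person-time is kept**

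The reported rate is λ(T − L)/T, which is 204/208 = 0.981 to 100/104 = 0.962 of the post-loading rate. This is an understatement of 2% to 4% before any difference in bleeding is considered.

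**The case against.** The strongest reply is that the exclusion is prespecified, openly stated in both sections and reasonable: a run-in before steady state is commonly left out of a steady-state estimate. That stands. The exclusion is not itself an error, and the post-loading rate should be kept.

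A reader might also infer that the adverse event rules keep disease-related bleeds out of safety, so that bleeds during the switch count in neither analysis. The documents do not support this as a general statement:

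- The carve-out in 6.11.1 does not name bleeds, is judged mostly on imaging, and sends any doubtful event to adverse event reporting.
- The definition in 6.11.1.2 applies regardless of attribution and includes new hemophilia signs and symptoms. The bullet that leaves out the studied disease is one item in an inclusive list.
- Section 6.11.3.2c counts worsening of a preexisting condition, with no exception for the disease under study.
- Section 6.11.2.2 names emergent surgery or amputation for uncontrolled bleeding. Section 6.11.3.2d makes an adverse event that leads to admission serious. Section 2.2 puts lack of efficacy within the safety objective.
- Adverse events are assessed around every loading dose.

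What remains is the silence on breakthrough bleeds as such, and the narrow route for events judged to be plain progression.

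Two other readings go too far. The definition does not cover all bleeds; it is limited to pseudotumor-related ones that need other treatment. Nor must the exclusion flatter the drug: person-time can leave with the events, the pre-study period has no loading phase to remove, and with k below 1 the from-first-dose rate would be the lower one.

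**Conclusion.** The point holds in a limited form. The analysed rate is not the rate that the objective defines, the difference falls on the switch period, and neither 9.5, 9.6 nor 9.7 gives a loading-phase rate. A loading-phase event judged to be plain progression may count in neither efficacy nor safety.

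The omitted time is small, at 1.9% to 3.8% of planned treatment. The effect on the on-study rate depends entirely on the assumed k: nil at k = 1, about 2-4% at k = 2, 8-15% at k = 5 and 17-35% at k = 10. A reader might take the upper figures as the expected distortion. The documents do not support that, because they give no pseudotumor-related bleed rate, and subjects on FVIII prophylaxis keep it until the second loading dose. Still, the protocol expects very few bleeding events in about 10 subjects, so a handful of dropped bleeds could be visible in the result. The study is descriptive, so no test or threshold is at risk. This is a cheap improvement in reporting that removes a real conflict between endpoint and analysis.

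**What to change.** In 9.5 and 9.6:

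- Keep the post-loading rate as the steady-state estimate. State the day on which counting starts, and that events and person-time are excluded together.
- Report beside it the rates of bleeds, admissions and anemia counted from the first dose, which matches the definition of hemostatic efficacy.
- Add one row for weeks 0-4 with events and person-time. Show the prior regimen in the subject listing rather than splitting the row, since cells will be very small with about 10 subjects.
- State that loading-phase bleeds appear in this row whether or not they are recorded as adverse events. This closes the gap left by 6.11.1 and 6.11.3.2k.

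The cost is a few sentences and one table row. No new data are needed: Sections 5.6 and 6.10 already have every bleed recorded in the diary, and admissions and anemia needing transfusion or intervention sent to the study center within 7 days. The downside is that the from-first-dose rate may look slightly less favourable.
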